9. STUDY ENDPOINTS

9.1 Primary Endpoint

Change in small artery elasticity (a marker for endothelial function) from baseline to 9 months after intervention initiation.

9.2 Secondary Endpoints

9.2.1 Change in Rasmussen Disease Score (RDS) from baseline to 9 months after intervention initiation. Each test is scored as 0 for normal, 1 for borderline, and 2 for abnormal. The criteria for normal, borderline, and abnormal has been established on the basis of large public databases. The ten cardiovascular tests provide total scores ranging from 0 (low risk) to 20 (high risk).

9.2.2 Change in each of the CDS components as measured from baseline to 3 and 9 months.

- Blood pressure at rest
- Large artery elasticity
- Treadmill exercise test
- Carotid intima-medial thickness
- Electrocardiogram (ECG)
- Left ventricle ultrasound
- Retinal vasculature
- Microalbuminuria
- NT-proBNP

9.2.3 Change in risk factor and biomarker measurements as measured from baseline to 3 and 9 months.

- Total cholesterol, LDL, HDL, and triglycerides
- hsCRP
- blood glucose

9.2.4 Difference in endothelial function quantification and sensitivity to change between pulse contour analysis and flow-mediated dilation from baseline to 9 months after intervention initiation.

10. ADVERSE EVENT REPORTING

For serious adverse event reporting purposes, toxicity information will be collected beginning with the 1st dose of study drug and continuing to approximately 30 days after the last dose of study drug or at the time the patient switches to commercially available drug (if patient decides to continue treatment beyond 1 year off study).

10.1 Definitions

Federal regulations [45CFR46.103(b)(5) and 21CFR56.108(b)(1)] require the IRB to ensure that researchers promptly report “any unanticipated problems involving risk to subjects or others” (UPIRTSOs). The IRB defines a UPIRTSO as any problem or event which in the opinion of the local researcher was unanticipated, reflects new and increased risk to the subjects, and was possibly related to the research procedures.

Problems/events that are unanticipated and involve new or increased risk to subjects should be reported *only* if in the opinion of the local researcher they are **possibly, probably or definitely related** to the research procedures.

10.2 Reporting Requirements

Agency	Criteria for reporting	Timeframe	Form to Use	Submit to:	Copy AE to:
U of MN IRB	Pose new or increased risk, unexpected, at least possibly related	10 Working Days	UPIRTSO form found on the IRB's Web site at http://www.research.umn.edu/irb/download/ .	MMC 820	Study file

10.3 Additional Events Requiring Reporting To the IRB

In addition the following events/problems meet the IRB's definition of UPIRTSO and should be reported to the IRB (but not the DSMC) within the 10 working day time frame:

- Any event (including on-site and off-site adverse events, injuries, side effects, deaths or other problems) which in the opinion of the local investigator was unanticipated, involved new or increased risk to subjects or others, and was possibly related to the research procedures;

- Any accidental or unintentional change to the IRB-approved protocol that increases risk or has the potential to recur;
- Any deviation from the protocol taken without prior IRB review to eliminate apparent immediate hazard to a research subject;
- Any publication in the literature, safety monitoring report (including Data and Safety Monitoring Reports), interim result or other finding that indicates an unexpected change to the risk/benefit ratio of the research;
- Any breach in confidentiality that may involve risk to the subject or others;
- Any complaint of a subject that cannot be resolved by the research staff; or
- Any other possibly related event which in the opinion of the investigator constitutes an unanticipated risk.

10.4 Events Not Requiring Reporting Until Time Of Annual Review

Those unanticipated problems/events that reflect new or increased risk to the subjects that the local investigator deems unlikely or not related to the research procedure DO NOT meet the IRB's definition of UPIRTSO and should be reported in summary form (using a table or spreadsheet) only at the time of IRB continuing review. Accompanying documentation (sponsor report forms, etc.) should NOT be included with this summary. If received, such accompanying documentation will be returned to the investigator.

10.5 Reporting of SAEs to Forest Research Institute (FRI)

Serious Adverse Event (SAE)

A serious adverse event is one that:

- Results in death
- Is an immediate threat to life
- Requires inpatient hospitalization, or prolongation of existing hospitalization
- Results in persistent or significant disability/incapacity
- Is a congenital anomaly or birth defect.

Causality Assessment

For all AEs, the Investigator must provide an assessment of causal relationship to the IP. Causal relationship must be assessed by answering the following question:

Is there a reasonable possibility the IP caused the event?

Yes: There is a possible or probable relationship (ie, there is a reasonable or strong temporal relationship, and the events are unlikely to be attributable to other drugs, underlying diseases, or other factors). Dechallenge and/or rechallenge (if available) is positive.

No: The relationship is unlikely or nonexistent (ie, there is no strong temporal relationship and/or the use of other drugs, underlying diseases, or other factors provide plausible explanations for the event), or the patient did not take the IP.

The Sponsor (Principal Investigator) is required to inform Forest Global Drug Safety of all SAEs. Forest Global Drug Safety must be notified immediately regarding any SAE that occurs after informed consent is obtained.

The Principal Investigator must report the event within 24 hours of first knowledge of any AE that meets one of the criteria for an SAE, to Forest Global Drug Safety on an SAE report form. If, during follow-up, any nonserious AE worsens and eventually meets the criteria for an SAE, that AE should be recorded as a new SAE.

The study center must transmit the SAE report form to the SAE [contact]** within 24 hours of first awareness of the event at the study center.

Supplemental information shall be submitted as soon as available and may include laboratory results, radiology reports, progress notes, hospital admission and emergency room notes, holding and observation notes, discharge summaries, autopsy reports, and death certificates.

Reporting of Pregnancy to Forest Research Institute

Study center personnel must report every pregnancy on a pregnancy report form as soon as possible (within 24 hours of first awareness of the pregnancy to the pregnancy fax number, **[contact]**), even if no AE has occurred, and follow it to term. If, however, the pregnancy is associated with an SAE (eg, if the mother is hospitalized for dehydration), in addition to the pregnancy report form, a separate SAE report form must be filed.

Fax all relevant SAE or pregnancy information to Forest Global Drug Safety. Contact information for Forest Global Drug Safety, personnel is as follows:

FOREST GLOBAL DRUG SAFETY DEPARTMENT
[contact]

11. DATA AND SAFETY MONITORING PLAN

Weekly meetings of the study's principal investigator and staff will be held to discuss matters related to the safety of protocol participants, validity and integrity of the data, enrollment rate, retention of participants, adherence to protocol, and data completeness.

12. STATISTICAL CONSIDERATIONS

This is a randomized, double-blinded, placebo-controlled Phase II study to obtain a preliminary estimate of the effects of nebivolol compared to atenolol and placebo on endothelial function (measured by arterial elasticity) and cardiovascular disease risk (measured by RDS).

12.1 Statistical Methodology

The primary analysis of the study is descriptive, to obtain a point estimate and 95% confidence interval of the difference in small artery elasticity (C_2) between nebivolol and atenolol treatment arms and nebivolol and placebo at the end of the observation period (9 months). Point estimates and 95% confidence intervals for the improvement in C_2 within each treatment will also be presented.

Secondary analysis estimating difference in Rasmussen Disease Score (RDS) improvement between the nebivolol and atenolol treatment groups along with nebivolol and placebo groups at the end of the observation period (9 months) will also be completed.

Other secondary analyses include estimates of the associations among changes in RDS as well as risk factor and biomarker measurements from baseline to the 3, and 9 month time points in the two positive comparator groups.

Unpaired t-tests will be used to compare the means of C_2 (small artery elasticity) as well as all RDS test component and biomarker values for each subject group at each time point. Paired t-tests will be used to compare baseline values and values from subsequent time points within one group. A P-value of < 0.05 will be considered statistically significant.

Comparison of sensitivity and variability for C₂ and flow-mediated dilation (FMD) methodologies used in quantifying endothelial function of each group over the 9 month study period will also be included in the secondary analyses. Data will be analyzed within and between test groups with a significance level of $P \leq 0.05$.

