A double-blind, placebo-controlled, randomized study examining the effects of nebivolol compared to atenolol on endothelial function and cardiovascular risk in patients with early vascular disease.

EVIDENCE: Early Vascular Impairment-Determine Efficacy of Nebivolol, Comparator Examination

Principal Investigator: [name]

Co-Investigators: [name], PhD
[name]
[name]

Version Date: January 14, 2014

University of Minnesota Medical School, Cardiology Division

PI Contact Information:

Mail: [name]
[name]

[contact]

[contact]

e-mail: [contact]

Table of Contents

STUDY SCHEMA	3
1. INTRODUCTION AND SCIENTIFIC RATIONALE	4
2. STUDY DESIGN	4
3. METHODOLOGY	4
4. OBJECTIVES	5
5. SELECTION OF PATIENTS	6
6. RANDOMIZATION PROCEDURES	7
7. TREATMENT PLAN	8
8. STUDY PARAMETERS	10
9. STUDY ENDPOINTS	12
10. ADVERSE EVENT REPORTING	13
11. DATA AND SAFETY MONITORING PLAN	16
12. STATISTICAL CONSIDERATIONS	16
13. ADMINISTRATIVE REQUIREMENTS	17
14. REFERENCES	18

STUDY SCHEMA

[figure not shown]
Study Population:

- Males and females between 18 and 80 years of age with early vascular disease
- Borderline blood pressure (120-145/80-90 mm Hg)
- Borderline or abnormal small artery elasticity (C_2) as measured by pulse contour analysis
- Treatment-naïve for all blood pressure medications including diuretics for at least 30 days prior to baseline visit
- No known history of cardiovascular disease

Accrual Goals:

75 patients enrolled.

Treatment Plan:

Schedule of Assessments:

- **Blood pressure at rest at 0, 1, 3, 6 and 9 months**
- **Small artery elasticity (C_2) and flow-mediated dilation at 0, 1, 3 and 9 months**
- **Rasmussen Disease Score assessments** (large artery elasticity, carotid intima-medial thickness, electrocardiogram (ECG), treadmill exercise test and left ventricle ultrasound) **at 0, 3 and 9 months**
- **Cardiac Health Biomarkers** (Total cholesterol, LDL, HDL, triglycerides, glucose, hsCRP, microalbuminuria and NT-proBNP) **at 0, 3 and 9 months**

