3. METHODOLOGY

The Rasmussen Disease Score (RDS) test panel is the chosen methodology for this study. The 10 parameters of the RDS were selected because of their ability

to quantify early structural and functional abnormalities in the vasculature and left ventricle which appear long before cardiovascular disease is present [8].

The RDS tests include: large and small artery elasticity (measured by pulse contour analysis), resting blood pressure, mild treadmill exercise test, carotid IMT, left ventricle mass, ECG, retinal vasculature evaluation, as well as quantification of serum NT-proBNP, and microalbuminuria. Please see Section 8 for a more detailed description of these parameters. Quantitative results from these tests are converted into categorical classifications based on values stratified by age and gender when appropriate. The categorical data is scored as follows: normal = 0 points, borderline = 1 point, abnormal = 2 points. Point values from all parameters are summed to create the RDS, with values ranging from 0-20. Scores of 0-2 are classified as normal, 3-5 as early disease, and 6+ as advanced disease. Previous research has shown that the RDS is a powerful predictor of future cardiovascular events [9].

The small artery elasticity (C_2) parameter is of particular interest as it is responsive to changes in NO levels [10] and is an effective and reliable predictor of future hypertension [11] and other cardiovascular events [12]. Changes in C_2 will serve as the primary outcome of this study. Similar studies using anti-hypertensive or lipid-lowering interventions have found significant improvements in C_2 values [13, 14].

Brachial artery flow-mediated dilation (FMD) measurements will also be measured as an index of endothelial function [15], although this method appears to be less sensitive to functional changes related to NO bioavailability than C_2 [10]. Utilizing both FMD and C_2 will allow comparison with previous studies and take advantage of a large sample size to further examine the relative sensitivity of each method for reliably measuring endothelial dysfunction.

The duration of intervention for this study is 9 months which is the minimum time to adequately detect improvement in left ventricle (LV) mass values. LV mass measurements are a critical component of a comprehensive assessment of cardiovascular health and have improved within this temporal window as a result of anti-hypertensive intervention [14, 16].

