8. STUDY PARAMETERS

8.1 Schedule of Events

Procedure/measurement	Screen	Baseline	1 Month	3 Months	6 Months	9 Months
Resting blood pressure	x		x	x	x	x
Arterial elasticity (small and large)	x		x	x		x
Treadmill exercise test		x		x		x
Carotid intima-medial thickness		x		x		x
Electrocardiogram		x		x		x
Left ventricle ultrasound		x		x		x
Retinal photo		x		x		x
Flow-mediated dilation		x	x	x		x
Blood draw		x		x		x
Urine sample collection		x		x		x
Physical examination		x		x		x
Medical history		x				

Blood and urine analysis	Code	Baseline	1 Month	3 Months	6 Months	9 Months
Pro-brain natriuretic peptide	ProBNP	x		x		x
Microalbumin, urine	UMA	x		x		x
high sensitivity C-reactive protein	hsCRP	x		x		x
Lipid panel	BLIP	x		x		x
Fasting glucose	Glu	x		x		x
Urine pregnancy test (if appropriate)	HCGU	x				

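### The primary endpoint is change in C2, but section 12.1 words the between-arm estimate as C2 at 9 months, unadjusted; one baseline-adjusted model would settle this and probably narrow the interval modestly.

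*Combined protocol and SAP*

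**What the plan says.** Section 3 states "Changes in C_2 will serve as the primary outcome of this study". Section 9.1 defines the primary endpoint as "Change in small artery elasticity (a marker for endothelial function) from baseline to 9 months after intervention initiation".

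Section 12.1 calls the primary analysis descriptive, a point estimate with a 95% CI, and gives its target as "the difference in small artery elasticity (C_2) between nebivolol and atenolol treatment arms and nebivolol and placebo at the end of the observation period". Change appears for C2 only within arms: "Point estimates and 95% confidence intervals for the improvement in C_2 within each treatment will also be presented". The only between-arm test named is in a later paragraph: "Unpaired t-tests will be used to compare the means of C_2 (small artery elasticity) as well as all RDS test component and biomarker values", at each time point. For the Rasmussen Disease Score (RDS) the same section does use change wording between arms: "Secondary analysis estimating difference in Rasmussen Disease Score (RDS) improvement between the nebivolol and atenolol treatment groups".

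Section 6 stratifies randomization by statin use and requires C2 to be measured before randomization. Section 12.1 uses neither in a between-arm comparison. Section 12.2 assumes an SD of 3.57 without saying whether it is the SD of C2 level or of change.

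The Study Schema lists "Small artery elasticity (C_2) and flow-mediated dilation at 0, 1, 3 and 9 months". The table in section 8.1 marks arterial elasticity at Screen and leaves the Baseline column blank.

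**The concern.** Two analysts could follow this plan and report different primary results: one the difference in 9-month C2, the other the difference in change. The section 12.1 wording reads as a contrast of levels, and the RDS sentence shows that change wording was available. A change contrast is still not ruled out. Because the study's main product is one estimate and its interval, that choice should not be left open until the data are in.

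The two readings have the same expected value under randomization but different precision, and neither is better at every correlation. Both leave out a pre-treatment C2 that every randomized patient should have. Both also leave out a stratification factor that section 5.3 says affects arterial elasticity.

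**Working it through.** **Inputs.** From section 12.2: 25 per arm, difference 3.3, SD 3.57, alpha 0.05 (taken as two-sided), power 0.9. From section 6: three arms, 1:1:1. Not in the documents, so assumed and varied: the correlation between pre-treatment and 9-month C2, and the C2 cutoff implied by the entry criterion in section 5.1.

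**The plan's own figure.** n = 2(1.960 + 1.282)² × (3.57/3.3)² = 24.6, so 25 per arm. Power at 25 is 0.905 by the normal approximation and 0.893 by the exact t. The stated sample size reproduces.

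**Unadjusted t-test on 9-month C2 (48 df).** SE = 3.57 × √(2/25) = 1.010. Half-width = 2.011 × 1.010 = 2.03.

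**Three-arm ANCOVA (70 df, two covariates).** Half-width = 1.994 × 1.010 × √(1 − r²) × √(1 + 2/69) = 2.043 × √(1 − r²), where r is the correlation within the trial.

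**Effect of selecting on C2.** Let R be the correlation in an unselected population with equal SDs at both times, and v the fraction of baseline variance left after selection. For a normal baseline cut to its lower half, v = 1 − 2/π = 0.363. Then r = R√v / √(R²v + 1 − R²). At R = 0.5, r = 0.301/0.917 = 0.33, and the half-width is 2.043 × √(1 − 0.33²) = 1.93.

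**Change-score t-test under the same selection.** SD = 3.57 × √{[(1 − R)²v + 1 − R²] / [R²v + 1 − R²]}. At R = 0.3 this is 3.57 × √(1.088/0.943) = 3.83, giving a half-width of 2.18.

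| R | r in trial | 9-month t-test | Change t-test | ANCOVA | ANCOVA vs 9-month t-test | ANCOVA power |
|---|---|---|---|---|---|---|
| 0.3 | 0.19 | 2.03 | 2.18 | 2.01 | 1% narrower | 0.899 |
| 0.5 | 0.33 | 2.03 | 2.03 | 1.93 | 5% narrower | 0.920 |
| 0.7 | 0.51 | 2.03 | 1.80 | 1.76 | 13% narrower | 0.958 |

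The literal section 9.1 analysis, an unadjusted change score, is about 7% wider than the 9-month t-test at R = 0.3 and wider than ANCOVA in all three rows.

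**Other assumptions.**
- Lower-quarter cutoff (v = 0.242): gains of about 0.6%, 3% and 9%. Lower three quarters (v = 0.535): about 2%, 7% and 18%.
- If 0.3, 0.5 and 0.7 are already within-trial correlations: half-widths 1.95, 1.77 and 1.46, or 4%, 13% and 28% narrower.
- Downside: at r = 0 the ANCOVA half-width is 2.04, which is 0.6% wider. Break-even is r = √[1 − (2.0302/2.0429)²] = 0.11.
- Statin stratum (simulated; half the sample on statins, assumed): if users differ by 1 or 2 units, the gain at R = 0.3 rises from 1.5% to 2.6% or 5.4%, and at R = 0.5 from 5.5% to 6.3% or 9.3%.

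**If 3.57 is the SD of change in an unselected population.** The level SD there is 3.57/√[2(1 − R)]. With the lower-half cutoff, the trial's 9-month SD is 3.27, 3.50, 3.82 and 4.35 at R = 0.5, 0.6, 0.7 and 0.8. The 9-month t-test then has power 0.937, 0.904, 0.849 and 0.749; ANCOVA has 0.956, 0.944, 0.931 and 0.918.

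**Simulation** (6,000 trials per setting, lower-half baseline) gave ANCOVA half-widths of 1.99, 1.91 and 1.74 against 2.02 for the 9-month t-test. Absolute bias was below 0.03 for both.

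**The case against.** The strongest reply is that nothing here is invalid. Both contrasts are unbiased, section 12 calls the trial preliminary, and the planned power reproduces. The t-test sentence is not tied to the primary interval, and the primary sentence read beside section 9.1 could mean change. All of this is correct. It limits the point to clarity and precision, but it also confirms that the text does not settle which contrast is meant.

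The size of the gain can also be challenged:
- Part of it comes from pooling the variance over three arms. Against a t-test that already does so (72 df, half-width 2.01), the gains are 0.3%, 4.2% and 12.6%. With the lower-quarter cutoff at R = 0.3 there is a 0.3% loss (2.019 against 2.013). Break-even moves to a within-trial r of about 0.17, and the cost at r = 0 to 1.5%.
- Section 12.2 expects a smaller SD here because patients are selected on C2. If 3.57 is the unselected level SD, the same cutoff gives 3.47, 3.27 and 2.96. The plain t-test then has power 0.910, 0.937 and 0.971, against 0.915, 0.956 and 0.994 for ANCOVA.

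Both points stand. The recommendation is therefore not a rescue of power, and the gain could be negligible if the correlation is low.

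The baseline question is mostly one of labelling. Section 6 requires C2 before randomization and section 8.1 shows a single pre-treatment value, at Screen, which is probably the month 0 value in the schema. Statin use is controlled by stable dosing and stratification, so leaving it out of the model does not bias the contrast; it only forgoes precision.

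**Conclusion.** The concern holds and should be fixed. The mismatch between sections 3 and 9.1 and section 12.1 is certain, as is the absence of any baseline or stratum adjustment between arms. There is no bias.

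The precision gain is modest and conditional. On the leading assumptions (population correlation 0.3 to 0.7, lower-half cutoff, 3.57 as the SD of 9-month C2) the interval is about 1% to 13% narrower. Across the other cutoffs and within-trial correlations shown, the gain runs from about nil to 28%, and the worst case is an interval about 1% wider. The correlation, the cutoff and the statin figures are all assumptions. The case for ANCOVA does not depend on a large gain: it gives one answer whether the response is 9-month C2 or change. The meaning of 3.57 and the Screen versus month 0 label are minor clarifications.

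**What to change.** - **Section 12.1:** make the primary estimate one three-arm ANCOVA of 9-month C2 on arm, with pre-treatment C2 and statin stratum as covariates. Report the adjusted nebivolol−atenolol and nebivolol−placebo differences with 95% CIs. State that using change in C2 as the response gives the same treatment estimate.
- **Section 9.1:** align the endpoint wording with that model.
- **Section 8.1 and the Study Schema:** reconcile C2 at month 0 with C2 at Screen, and name the pre-treatment value to be used.
- **Section 12.2:** state whether 3.57 is the SD of C2 level or of change.

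This needs no new data, visits or patients. The statistical cost is two degrees of freedom, about 1% in interval width if the correlation is near zero.

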12.2 Design and Sample Size Justifications

A sample size of 25 subjects per arm will be adequate to detect a difference in small artery elasticity of 3.3 units (ml/mm Hg x 100) between positive comparators when power = 0.9 and $\alpha = 0.05$. This is assuming a standard deviation of ± 3.57 units. This assumption is made based on a previous clinical trial measuring small artery elasticity in patients undergoing anti-hypertensive therapy [14].

Subjects in the previous study were not selected on the basis of C₂ as they are in EVIDENCE. Therefore, it is reasonable to assume that our actual standard deviation will be much smaller than our estimate giving us a conservative population sample of 75. Assuming a smaller deviation of 3.0 (instead of 3.57) we would still have an adequate sample with a dropout rate of 7.6%. If rates of attrition exceed 7.6%, subjects will be replaced

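### Section 12.1 names t-tests of means, with no log scale or baseline adjustment, for biomarkers likely to be strongly right-skewed (hsCRP, NT-proBNP, urine microalbumin), which costs efficiency in secondary analyses

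*Combined protocol and SAP*

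**What the plan says.** Section 12.1 gives one inferential method for the continuous measurements. It opens with "Unpaired t-tests will be used to compare the means of C_2 (small artery elasticity" and extends the same test to the other measurements, "as well as all RDS test component and biomarker values for each subject group at each time point". Within an arm, "Paired t-tests will be used to compare baseline values and values from subsequent time points within one group". The threshold is common to all of them: "A P-value of < 0.05 will be considered statistically significant". The section mentions no transformation, geometric mean, rank test, distribution check or adjustment for baseline.

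The variables covered include hsCRP and triglycerides under 9.2.3, whose endpoint is "Change in risk factor and biomarker measurements as measured from baseline to 3 and 9 months", and NT-proBNP and microalbuminuria, listed as components under 9.2.2. Section 3 has NT-proBNP and microalbuminuria quantified, then converts every RDS test to a 0, 1 or 2 score before summing. Section 8.1 schedules all four markers at baseline, 3 and 9 months, so a baseline value is planned for each.

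The sample size in 12.2 is for C2 only: "A sample size of 25 subjects per arm will be adequate to detect a difference in small artery elasticity of 3.3 units". No power is claimed for any biomarker.

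**The concern.** hsCRP, NT-proBNP and urine microalbumin are positive concentrations that commonly have a long right tail. In a group of 25, one or two high values can dominate the mean and its standard error. A drug effect on such a marker is also more naturally proportional than additive. A t-test of untransformed means is then an inefficient way to look for it, and a test of 9-month values alone also discards the information in the baseline measurement.

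At stake are the secondary comparisons of these markers under objectives 4.2.2 and 4.2.3. A real effect could be missed because of the choice of scale and model, when the data needed for a better analysis are already being collected.

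**Working it through.** **1. The plan's own figure.** Inputs from 12.2: difference 3.3, SD 3.57, power 0.90, alpha 0.05 (two-sided assumed).

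n per arm = 2 × (1.960 + 1.282)² × 3.57² / 3.3² = 24.6, rounded up to 25.

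The stated 25 reproduces (power 0.905; with the exact t distribution, 25.6 per arm and power 0.893 at 25). It says nothing about the biomarkers.

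**2. Assumptions for the biomarkers.** The documents give no SD, distribution or effect for any of them, so all of these are assumed: lognormal values; equal log-SD in both arms, at 0.8, 1.0 or 1.2; log-scale correlation of 0.7 between baseline and 9 months; true reduction of 40% or 20%; two-sided 0.05; 25 per arm with no dropout.

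**3. Expected signal on the log scale.** A 40% reduction is a log difference of −ln(0.6) = 0.511. The standardised signal of the two-sample test is 0.511 / (log-SD × √(2/25)):
- log-SD 0.8: 0.511 / (0.8 × 0.2828) = 2.26
- log-SD 1.0: 1.81
- log-SD 1.2: 1.51

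Adjusting for log baseline multiplies the residual SD by √(1 − 0.7²) = 0.714, so the signals become 3.16, 2.53 and 2.11.

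**4. Simulated power, 40% reduction, 9-month values between two arms.** The raw-scale test has no simple formula, so all three analyses were simulated. Repeating the simulation with 40,000 trials per setting gave the same values to within 0.01.

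| Log-SD | Raw t-test (12.1 as read) | Log t-test | Log, adjusted for log baseline |
|---|---|---|---|
| 0.8 | 0.48 | 0.60 | 0.86 |
| 1.0 | 0.30 | 0.43 | 0.69 |
| 1.2 | 0.19 | 0.31 | 0.53 |

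The log scale alone adds 12, 13 and 12 points. Baseline adjustment on that scale adds a further 26, 26 and 22, so the larger part of the gain comes from using the baseline.

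**5. Smaller effect, 20% reduction.** At log-SD 0.8/1.0/1.2 the raw test has power 0.13/0.09/0.06 and the log test 0.16/0.12/0.10. The adjusted log analysis reaches at most 0.27.

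**6. Within-arm paired test.** The effect is set so that the log-scale paired test has 80% power, with correlation 0.5 to 0.7. Raw-scale power is then 61–63% at log-SD 0.8, 52–55% at 1.0 and 44–46% at 1.2.

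**7. Type I error of the raw unpaired test.** It is 0.047 at log-SD 0.5, 0.040 at 1.0 and 0.036 at 1.2, so it is not inflated.

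**8. Triglycerides, assumed log-SD 0.4–0.5.** For 9-month values with a 40% reduction, raw against log is 0.99 against 0.99 at log-SD 0.4, and about 0.92 against 0.94 at 0.5. With a 30% reduction it is 0.84 against 0.87, and 0.65 against 0.70. The between-arm loss is about 0–5 points. The paired test at log-SD 0.5 falls from 80% to 72–73%.

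**9. Values below the assay limit.** Suppose half of the control values lie below the limit and are set to half of it. A true ratio of 0.50 is then estimated as about 0.64–0.66 (log-SD 0.8–1.2). Simple substitution pulls the ratio toward 1.

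**The case against.** Several points on the other side have force.

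- *The scale is inferred from silence.* Section 12.1 never says untransformed, and a t-test on logs is still a t-test of means. This stands, although a comparison of means of values reads most plainly as the raw scale, and either way the sentence needs the scale stated.
- *Every spread and effect is assumed.* This stands. Section 5.2 excludes known diabetes, renal disorder and cardiovascular disease, which may shorten the tails, and nothing in the documents supports an effect as large as 40%. With a 20% reduction no choice of analysis rescues these comparisons.
- *These are secondary analyses.* The study seeks a preliminary estimate, its primary analysis is descriptive, and 12.2 claims no power for biomarkers. This limits the weight of the point but does not remove it, because 12.1 still applies a 0.05 threshold to these markers.
- *Section 12.1 does not say whether RDS components are tested as quantities or as 0/1/2 scores.* If as scores, the argument covers hsCRP only. Section 3 calls for quantification, so the quantities should exist.

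A reader might also infer more than the documents support:

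- *That the loss from the scale alone is 30–33 points.* That gap appears if change from baseline is compared between arms (raw 0.50/0.30/0.18 against log 0.82/0.63/0.48, for a 40% reduction). Section 9.2.3 does define the endpoint as change, but the unpaired test in 12.1 is of values at each time point. For that test the scale alone costs 12–13 points.
- *That the RDS result or the false-positive rate is compromised.* Neither is: the total uses categories, and type I error stays below 5%.
- *That triglycerides, or all of objective 4.2.3, are affected to the same degree.* Triglycerides lose little between arms, and nothing here concerns total cholesterol, LDL, HDL or glucose.

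**Conclusion.** The point holds for hsCRP, NT-proBNP and urine microalbumin. The method in 12.1, read as a raw-scale comparison without baseline adjustment, is less efficient than one that needs no extra data. Under the stated assumptions and a 40% reduction, moving to a baseline-adjusted log-scale analysis raises power by 38, 39 and 34 points at log-SD 0.8, 1.0 and 1.2 (0.86 − 0.48, 0.69 − 0.30, 0.53 − 0.19). Those figures depend on lognormality, a proportional effect and the assumed correlation of 0.7, none of which the documents supply. The consequence is lost efficiency in secondary analyses, not bias or invalid inference. It is worth correcting because the correction is cheap.

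**What to change.** In 12.1, state that hsCRP, NT-proBNP and urine microalbumin are analysed as quantities on the log scale, with the log baseline value as a covariate. Report the comparisons of nebivolol with atenolol and with placebo as ratios of geometric means with 95% confidence intervals. Triglycerides may be treated the same way, but this is optional.

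State how values below the assay limit are handled. If there are many, add a censored-data (Tobit) or rank-based analysis as a check, and do not rely on substituting half the limit.

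The cost is a change of wording: no extra patients, visits or samples. The downside is that the estimand becomes a ratio of geometric means instead of a difference in means. The choice should therefore be fixed before unblinding, so that the scale cannot be picked after seeing the results.
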